7.1.5 Primary Analysis of the Primary Efficacy Outcome

Associated exact 95% confidence intervals for the probability of reaching a positive response at each dose will be estimated for each dose using the Clopper-Pearson method for both the Phase 1a and Phase 2 cohorts.

TNSS, sneeze score, and other TNSS component scores will also be summarized over all participants at each dose with tables and boxplots. TNSS and sneeze score at each dose will additionally be listed and overlaid graphically for each subject. Attainment of the positive response thresholds for TNSS and sneeze score at each dose will additionally be analyzed with frequency tables.

7.2 Secondary Efficacy Outcomes

Participants stopped receiving doses once they reached a positive response, so all doses were not observed for each subject. This truncated nature of the data violates assumptions of standard statistical tests. In light of this issue, we will use descriptive statistics to assess secondary study hypotheses instead of formal hypothesis tests.

7.2.1 Secondary Efficacy Outcome 1 – Number of Sneezes

The number of sneezes will be summarized across participants in each of the Phase 1a and Phase 2 cohorts at each dose during the challenge. Frequency tables will be used to descriptively assess whether there is an association between dose and number of sneezes. Number of sneezes at each dose will additionally be listed and displayed graphically for each subject.

7.2.2 Secondary Efficacy Outcome 2 – Maximum TNSS Score Over All Doses

The maximum TNSS score over all doses received in each of the Phase 1a and Phase 2 cohorts will be summarized across participants and examined with 95% confidence intervals and boxplots. Maximum TNSS score will additionally be listed for each subject.

7.2.3 Secondary Efficacy Outcomes 3-8 – Change from Baseline in TNSS, PNIF, PEF, VAS, Tryptase in Nasal Secretions, and Albumin in Nasal Secretions.

For each of the six variables TNSS, PNIF, PEF, VAS, tryptase, and albumin, the baseline score will be defined as the value obtained at the post-rinse baseline assessment in the challenge. The post-baseline score will be the one associated with the highest dose received in the challenge. Change from baseline will then be computed as post-baseline minus baseline. Whether change is different from zero will be assessed for each of these variables for each of the Phase 1a and Phase 2 cohorts using 95% confidence intervals and boxplots. Values for each of the six variables at each dose will be listed and displayed graphically for each subject. TNSS, sneeze score, and PNIF as well as TNSS, sneeze score, and VAS will be overlaid together graphically for each subject.

Tryptase and albumin will be transformed using a natural logarithm prior to analysis, as necessary. The lowest and highest detectable values will be substituted for values below and above the measureable thresholds, respectively. The number and percent of values that are above or below detectable thresholds will be tabulated for each variable and phase using frequency tables.

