6.1.2. Dosage, Preparation, and Administration

Dilutions of the German cockroach allergenic extract needed for NAC dose escalation will be prepared by the site research pharmacy.

Participants will receive escalating doses of glycerinated German cockroach allergenic extract administered via the intranasal route. Each dose will be administered as a nasal spray with the use of a nasal drug delivery system (LMA/Teleflex, San Diego, CA), which delivers 0.1 mL per activation (spray). One spray will be delivered in each nostril for a total delivered volume of 0.2 mL. Nine doses will be given. Dose 1 will be a diluent control. Doses 2 through 9 will have a Bla g 1 dose range of approximately 0.002 mcg to 5 mcg.

All 8 allergen doses will be used in the first 5 children in Phase 2 to ensure a similar response pattern to that seen in the adults. If, like in the adults in Phase 1, none of these 5 children react to the first allergen dose, this dose will be dropped from the subsequent challenges. The threshold for a positive response to the NAC in Phase 2 will be defined as a TNSS ≥ 6 ; the sneezing score of 3 will remain the same.

The proposed NAC dose escalation for Phase 2 was reviewed and approved by the NIAID Allergy and Asthma DSMB.

Complete details of the dilutions can be found in the MOP for Protocol ICAC-27, which is based on the DAIT Pharmacy manual.

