8.3. Challenge Visit

Participants who are deemed eligible based on results from tests conducted at the Screening Visit will be invited to proceed to the Challenge Visit in Phase 1a and Phase 2.

The following procedures, assessments, and laboratory measures will be conducted:

1. Concomitant medications
2. Adverse events
3. Assessment of nasal and pulmonary symptoms (including spirometry)
4. Brief Physical Exam - includes Vital signs, height, weight and nasal and lung exam (or as specified in the MOP for Protocol ICAC-27)
5. Urine pregnancy test (female participants; if more than 28 days after the screening visit)
6. Initial nasal rinses – approximately 200mcl of isotonic saline solution (2 sprays) will be sprayed into each nostril and the participant will be asked to blow their nose; this process will be repeated 3 times (as specified in the MOP for Protocol ICAC-27). The fluids from the 2nd and 3rd rinses will be collected and processed for analysis as specified in the MOP for Protocol ICAC-27 – the outcomes from these fluids will be considered baseline for the ensuing nasal challenge procedure. A nasal rinse will be repeated 10 minutes after the diluent control is administered and after each dose of allergen during the NAC, as specified in the MOP for Protocol ICAC-27.
7. Nasal symptoms – TNSS and VAS and will be assessed pre and post the initial nasal rinses, and then 10 -20 minutes after each NAC dose administration and before the nasal rinse. (as specified in the MOP for Protocol ICAC-27) If the participant does not qualify for the Challenge because of the TNSS score, they may be rescheduled as per the MOP for Protocol ICAC-27.
8. Peak nasal inspiratory flow (PNIF) - assessed pre and post the initial nasal rinses, and then 10-20 minutes after each NAC dose administration (as specified in the MOP for Protocol ICAC-27)

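### SAP 7.2.3 tests change from a pre-diluent baseline against zero and plans no estimate against the diluent dose; for tryptase and albumin the two fluids are also collected differently.

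*SAP*

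**What the plan says.** SAP 7.2.3 covers change from baseline in TNSS, PNIF, PEF, VAS, tryptase and albumin.

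- Starting value: "the baseline score will be defined as the value obtained at the post-rinse baseline assessment in the challenge".
- End value: "The post-baseline score will be the one associated with the highest dose received in the challenge".
- Comparison: "Whether change is different from zero will be assessed for each of these variables", by cohort, with 95% CIs and boxplots.
- Display: "Values for each of the six variables at each dose will be listed and displayed graphically for each subject". Dose 1 values are therefore shown, but they enter no estimate.

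Protocol 6.1.2 states "Dose 1 will be a diluent control". It is given after the post-rinse assessment (Protocol 8.3), so the baseline is a pre-diluent one. Protocol 13.4.3 plans summary statistics, correlation analyses and changes from baseline, but no difference from diluent.

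On the biomarker samples, Protocol 8.3 item 6 says of the three initial saline rinses: "The fluids from the 2nd and 3rd rinses will be collected and processed for analysis", and "the outcomes from these fluids will be considered baseline for the ensuing nasal challenge procedure". It continues: "A nasal rinse will be repeated 10 minutes after the diluent control is administered and after each dose of allergen during the NAC". Item 11 adds that secretions are gathered for about 10 minutes after each diluent or allergen dose and are mixed with the fluid of the rinse that follows.

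**The concern.** The challenge includes a within-subject negative control, and the planned estimate of change does not use it. For anyone who receives allergen, the planned change splits exactly into two parts:

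last dose - baseline = (last allergen dose - Dose 1) + (Dose 1 - baseline)

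The second part contains no allergen effect. For PNIF it holds only the effect of the vehicle and of spraying. For tryptase and albumin it also holds the switch from a rinse-only sample to a rinse plus 10 minutes of secretions. No sampling mismatch arises for PNIF, and no timing mismatch is claimed for TNSS or VAS.

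Protocol 2.3 makes the validity of PNIF and of nasal-secretion biomarkers in children a secondary objective, and these changes are the planned summary estimates for those outcomes. From the planned CI for tryptase or albumin, a reader could not tell a response to allergen from a change in how the fluid was obtained.

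**Working it through.** **The plan's own figures.** The documents give no precision or power figure for these outcomes. The only such table (Protocol 13.6) gives exact CIs for a response proportion in 10 adults. All 11 rows reproduce at the printed precision, but they do not bear on this point.

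**Sample comparison (Protocol 6.1.2 and 8.3)**

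| Fluid | Saline instilled | Timed secretions | Preceding dose |
|---|---|---|---|
| Baseline (rinses 2 and 3) | 2 x 400 = 800 mcL | none described | none |
| After Dose 1 (diluent) | 400 mcL | about 10 min | 200 mcL |
| After each allergen dose | 400 mcL | about 10 min | 200 mcL |

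Each rinse is 200 mcL x 2 nostrils = 400 mcL. Dose 1 matches the allergen doses in collection; baseline does not.

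**How large could the collection effect be?** Processing is in the MOP, which is not available. Four dilution-only cases, ignoring secretion volume, give the ln ratio of post-dose to baseline concentration. A numerator of 1 or 2 is the assumed relative amount of marker recovered, and 600 mcL assumes the 200 mcL dose is fully recovered:

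- ln[(1/400)/(1/800)] = +0.69
- ln[(1/600)/(1/800)] = +0.29
- ln[(1/400)/(2/800)] = 0.00
- ln[(1/600)/(2/800)] = -0.41

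The sign is not determined, and zero is among the cases.

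**Effect on the planned CI, no early stopping.** Let T be noncentral t with n - 1 df and noncentrality (shift/SD) x sqrt(n). Then P(CI excludes 0) = P(|T| > t(0.975, n - 1)). The allergen effect is set to zero and the SD of the ln change is assumed.

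| n | Shift | SD 0.5 | SD 0.75 | SD 1.0 |
|---|---|---|---|---|
| 25 | +0.29 | 0.795 | 0.459 | 0.286 |
| 25 | -0.41 | 0.976 | 0.746 | 0.503 |
| 10 | +0.29 | 0.374 | 0.195 | 0.130 |
| 10 | -0.41 | 0.637 | 0.340 | 0.213 |
| either | 0 | 0.05 | 0.05 | 0.05 |

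Without stopping, last dose minus Dose 1 excludes zero in about 5% of trials, provided the shift is the same at both doses.

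**With stopping on symptoms (simulation, 3,000 to 5,000 runs per setting).** Assumptions: n = 25; Dose 1 plus 8 doses; stop at TNSS >= 6; mean TNSS 2 or 3; between-subject SD 1; within-subject SD 1 or 1.5; marker-TNSS within-step correlation 0 to 0.5; marker SD of difference 0.75; no allergen effect. Sneezing stops and baseline eligibility are not modelled. Participants who stop at diluent (mean 0.2 to 2.1 of 25) are dropped from the diluent contrast.

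| Outcome and shift | Baseline reference | Diluent reference |
|---|---|---|
| Marker, +0.29 | 0.46-0.83 | 0.05-0.20 |
| Marker, -0.41 | 0.31-0.76 | 0.04-0.20 |
| Marker, 0 | 0.05-0.20 | 0.04-0.21 |
| TNSS | 0.05-0.56 | 0.05-0.60 |

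The diluent reference removes the collection shift but not the selection caused by stopping on symptoms. A correlated marker keeps a bias of 0 to +0.19 ln units, and TNSS gains nothing.

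**Precision of the added contrast.** The half-width in SD units is t/sqrt(n): 2.064/sqrt(25) = 0.413, and 2.074/sqrt(23) = 0.432 if two children stop at diluent.

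**The case against.** The strongest reply is that the deciding details are out of sight. Protocol 8.3 sends fluid processing to the MOP, which may settle pooling, volume correction, and concentration versus total amount. One of the four dilution cases is exactly zero, all four ignore secretion volume, and two assume the whole dose is recovered. The documents therefore show different collection, not a demonstrated bias. This stands as a limit on size and direction. It does not restore zero as the reference, because volume correction would not remove a vehicle effect or the added secretion period, and SAP 7.2.3 mentions no correction.

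Second, SAP 7.2 declares the secondary analyses descriptive, and nothing makes exclusion of zero the test of validity. A shift common to all participants would also leave the correlations planned in Protocol 13.4.3 unchanged. Both points are true and keep the weight of the issue low. Even so, SAP 7.2.3 uses a CI to ask about zero, and a descriptive estimate still needs a meaningful reference.

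Third, Dose 1 data are already displayed. For PNIF and the biomarkers that means only per-subject listings and graphs; the per-dose tables in SAP 7.1.5 and 7.2.1 cover TNSS, its components and sneezes.

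Finally, the added contrast loses anyone who stops at diluent, which conditions on a post-dose outcome, whereas Protocol 13.4.1 places all analyses on the Safety Population. It also leaves stopping-rule selection and cumulative drift in place. These are real costs and the reason to add the contrast, not substitute it.

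**Conclusion.** The point holds. The planned change uses a pre-diluent reference and no contrast with the diluent control is planned. For tryptase and albumin, zero cannot be presumed to represent no allergen effect. That conclusion rests on the text alone.

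The numerical size is illustrative, since the shifts, SDs and correlations are all assumed. In the no-stopping calculation for 25 children, the chance that the CI excludes zero without any allergen effect runs from 5% with no artefact to 98% (shift -0.41, SD 0.5). If there is no artefact, the diluent contrast gains nothing.

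For PNIF the case is weaker and concerns only vehicle and repeated spraying. The primary outcome is untouched. This is a worthwhile, cheap improvement to secondary analyses, not a fault in the main result.

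**What to change.** Keep the protocol-defined change from post-rinse baseline in the full Safety Population. Add to SAP 7.2.3:

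1. For tryptase, albumin (on the ln scale where transformed) and PNIF, by cohort with 95% CIs: last allergen dose received minus Dose 1, and Dose 1 minus post-rinse baseline.
2. A statement that the diluent contrast is used to interpret allergen effect for tryptase and albumin; for PNIF it is read beside the baseline change.
3. For TNSS and VAS, the diluent contrast shown descriptively only.
4. A statement that stopping on TNSS partly fixes the final value under either reference and can carry over to correlated markers.
5. A count and listing of participants who stop at diluent, noting that they leave the diluent contrast but remain in the baseline-change analysis.

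The PEF baseline used for safety grading (Protocol Table 12.3.1b) stays as it is.

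The cost is SAP text and one extra set of tables from values already collected, plus a slightly wider interval if anyone stops at diluent. The contrast does not remove drift over repeated sprays and rinses.

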7.2.4 Secondary Efficacy Outcomes 9 – Reproducibility of the Primary Efficacy Outcome

The first dose at which a positive response occurs for an individual will be summarized for Phase 1b data in the same manner as in sections 7.2.1 and 7.2.2. The difference in the probability of reaching a positive response between Phase 1a and Phase 1b will be computed for each dose and summarized with 95% confidence intervals and boxplots. Frequency tables will be used to assess agreement between Phase 1a and Phase 1b in attainment of the positive response threshold.

8. Safety Evaluation

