11. Nasal allergen challenge (NAC) - increasing doses of allergen in defined time intervals (every 20 minutes) up to a specified maximum dose or symptom level, will be given as described in an accompanying MOP for Protocol ICAC-27. Briefly, one spray (100mcL) of diluent or diluted allergen solution is applied to each of the participant's nostrils using a nasal drug delivery system while the participant breath-holds at TLC. After the dose is delivered, the participant is asked to exhale through the nose and then to avoid sniffing or swallowing in the immediate 1 minute after application. In Phase 1, the challenge will begin with a 0 mcg/ml (negative control – 50% glycerin, 50% COCAS with 0.2% phenol) dose followed by up to 8 doses of increasing concentration, until the participant reaches a TNSS score of 8 or more, has a sneezing score of 3 or their symptoms become intolerable. In Phase 2, the challenge will begin with a 0mcg/ml (diluent control) dose followed by a number of doses of increasing concentration, until the participant reaches a TNSS score of ≥ 6 , has a sneezing score of 3 or their symptoms become intolerable. All 8 allergen doses will be used in the first 5 children in Phase 2 to ensure a similar response pattern to that seen in the adults. If, like in Phase 1 in adults, none of these 5 children react to the first allergen dose, this dose will be dropped from the subsequent challenges. Nasal secretions will be collected for approximately 10 minutes immediately following administration of each diluent and allergen dose and a nasal rinse (two 100mcL sprays of isotonic saline solution per nostril) will be performed at 10 minutes, as described above. The fluids from each rinse will be mixed with the nasal secretions collected during the preceding 10 minutes and processed for analysis as specified in the MOP for Protocol ICAC-27. Collection of other outcomes will begin 10 minutes after each diluent or allergen dose is administered. If a participant begins exhibiting asthma symptoms during the NAC, or the PEF is reduced by more than 20% from baseline, the challenge will be suspended, and the participant will be evaluated by the study clinician. If it is determined treatment is needed based on clinical judgment, then the challenge will not be continued. In the absence of an immediate need for treatment, spirometry will be performed to confirm a change in lung function. If the FEV1 is $< 85\%$ of baseline value, the challenge will be stopped. If spirometry is performed because of a low PEF and the FEV1 is $\geq 85\%$ of baseline value, the challenge can continue at the clinician's discretion.

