13.4.3 Analyses of Secondary and Other Outcomes

The secondary statistical analyses will include summary statistics for the secondary endpoints and correlation analyses. Changes from baseline levels of TNSS, PNIF, and PEF will be estimated in absolute and relative terms.

To assess reproducibility of the adult nasal challenge, the first dose at which a positive response occurs for an individual will be compared between study visits. A weighted Kappa statistic and associated 95% confidence interval will be estimated for each dose category to quantify agreement between study visits.

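### SAP 7.2.4 drops the protocol's weighted kappa for reproducibility and leaves no pre-specified within-person measure of agreement

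*SAP*

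**What the plan says.** Secondary objective 3 (Protocol 2.3) is to assess how reproducible the challenge is in adults. Protocol 13.4.3 gives it a within-person analysis: "the first dose at which a positive response occurs for an individual will be compared between study visits". The statistic follows: "A weighted Kappa statistic and associated 95% confidence interval will be estimated for each dose category".

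SAP 7.2.4 has three elements and no kappa:

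- A one-visit summary: "The first dose at which a positive response occurs for an individual will be summarized for Phase 1b data".
- A between-visit contrast: "The difference in the probability of reaching a positive response between Phase 1a and Phase 1b will be computed for each dose", with 95% CIs and boxplots. It does not say whether the interval is paired.
- Tables: "Frequency tables will be used to assess agreement between Phase 1a and Phase 1b in attainment of the positive response threshold". It does not say whether they are cross-classified within person or made dose by dose.

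SAP 4 defines one safety population, split into adult and child cohorts. It defines no set of adults challenged in both Phase 1a and Phase 1b.

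**The concern.** Reproducibility here asks whether the same adult reacts at the same dose on a second occasion. The protocol's planned statistic answers that, and the SAP removes it without comment.

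The nearest thing to a reason is the opening of SAP 7.2. It says that stopping dosing at a positive response breaks the assumptions of standard tests, so "we will use descriptive statistics to assess secondary study hypotheses instead of formal hypothesis tests". That does not reach a kappa with a CI, which is an estimate, and the SAP keeps 95% CIs throughout 7.2. Nor does the truncation hide the outcome: for a responder, the first positive dose is the event that stops dosing. It is unobserved only for non-responders and for adults who stop early without a positive response. Protocol 8.3 allows the latter, since a challenge runs until the participant reaches the TNSS threshold, "has a sneezing score of 3 or their symptoms become intolerable". Those cases need a top category and a coding rule.

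The remaining contrast compares cumulative response curves, because SAP 7.1.4 counts a responder as responding at all later doses. Such a contrast is a function of the two marginal distributions only. The tables might rescue the analysis if paired and by dose, but that is not written. SAP 7.1.5 does specify dose for its own tables ("Attainment of the positive response thresholds for TNSS and sneeze score at each dose will additionally be analyzed with frequency tables"); 7.2.4 does not.

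At stake is whether objective 3 ends with a pre-specified within-person estimate. If the intervals are unpaired and the tables record attainment at any dose, a repeatable and an unrepeatable challenge can produce the same planned output.

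**Working it through.** **The plan's own figures.** The documents give no precision figure for reproducibility. The only precision table is the exact-interval table in Protocol 13.6 (n = 10). Clopper-Pearson limits from beta quantiles reproduce all 11 rows to its rounding: for example 0/10 upper limit 0.3085 (stated 0.31), and 5/10 gives 0.187 to 0.813 (stated 0.19, 0.81).

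**Illustrative data (an assumption, not trial data).** Ten adults have Phase 1a first positive doses 3, 4, 5, 5, 6, 6, 7, 8, 9, none, with none coded 10. Cumulative responders at doses 3 to 9 are 1, 2, 4, 6, 7, 8, 9.

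Linear-weighted kappa = 1 − (observed mean absolute dose gap) / (mean gap expected from the margins). With both margins as above, the expected gap is 238/100 = 2.38.

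**Step 1: point estimates.**

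| Phase 1b pattern | Observed gap | Expected gap | Kappa | Largest per-dose difference |
|---|---|---|---|---|
| Exact repetition | 0 | 2.38 | 1.00 | 0 |
| Full reversal | 34/10 = 3.4 | 2.38 | 1 − 3.4/2.38 = −0.43 | 0 |
| Nine responders reversed, non-responder unchanged | 26/10 = 2.6 | 2.38 | −0.09 | 0 |
| Every responder up one dose | 9/10 = 0.9 | 2.42 | 0.63 | 20 points |

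In the third row a yes/no attainment table shows 10/10 agreement (9 yes-yes, 1 no-no). Yet only 4 of 10 adults are within one dose step, and the mean gap is 2.6 doses.

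**Step 2: how typical this is.** Equal margins are extreme. In 50,000 sets of Phase 1b doses drawn independently from the same ten values, all differences are zero in about 0.14%, and the median largest difference is 20 points. The comparison with one-step noise (25% down, 50% same, 25% up) is:

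| | Independent | One-step noise |
|---|---|---|
| Largest difference ≤ 10 points | about 31% | 84% |
| Kappa ≥ 0.5 | about 0.7% | 100% |

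The difference is therefore a weak indicator of repeatability, not a blind one. It also shows 20 points when every responder moves up exactly one dose, the same as its median under independence.

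**Step 3: intervals.** The unpaired Wald half-width is 1.96√(2p(1−p)/10). At p = 0.1 it is 0.263 and at p = 0.4 it is 0.429. It is the same for repetition and reversal, because p is the same. The paired Wald half-width is 1.96√(b+c−(b−c)²/10)/10, where b and c are the discordant counts. Under reversal, b = c = 1, 2, 4, 4, 3, 2, 1 at doses 3 to 9, giving 0.277 to 0.554; under repetition it is 0. A paired score interval gives 0.342 to 0.487 against 0.278. Pairing separates the two cases; the SAP does not specify it.

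**Step 4: denominator.** Protocol 3.1 expects all 10 adults to return. However, Protocol 4.2 and 4.3 set eligibility limits for Phase 1b, and 11.1 allows refusal. Suppose all ten Phase 1a adults are compared with returners who repeat exactly. One non-returner then creates a false largest difference of 4 to 10 points (if the non-responder is lost, dose 9 shows 9/10 against 9/9). Two create 5 to 20 points, and three create 6 to 30. In a paired set it is zero.

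**Step 5: coding.** Nine adults repeat exactly. One, positive at dose 5 in Phase 1a, stops after dose 3 in Phase 1b without a positive response. Coded as no response, kappa is 1 − 0.5/2.56 = 0.80. Coded at the last dose, it is 1 − 0.2/2.52 = 0.92. Excluded, it is 1.0.

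**The case against.** The strongest reply is that the harm rests on an unfriendly reading. Agreement between two challenges in the same people ordinarily implies a within-person cross-classification, and the sentence before the tables is about each dose. By-dose paired tables would expose full reversal: concordance would be 10 − (b + c), or 2 of 10 at doses 5 and 6. A boxplot also needs participant-level values, which hints that within-person differences were intended. Per-subject listings are planned, and with ten adults a reader could pair the results by hand.

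This is a fair account of what may have been meant. It does not supply a specified analysis: neither pairing nor dose is stated for the tables or interval, and a listing is not an estimate.

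Second, the dropped plan was itself loose. Protocol 13.4.3 asks for a kappa per dose category, without weights or a no-response category. That stands. Weights do nothing in a single yes/no category, and across ordered doses they matter: the pattern with every responder up one dose gives 0.63 with linear weights and 0.90 with quadratic. This argues for repairing the kappa, not for silently omitting it.

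Third, this is a descriptive pilot with at most 10 pairs, reproducibility is not among the eight listed secondary outcomes, and Protocol 3.1 makes Phase 2 independent of Phase 1b. All true, and it limits the importance. The early-stopping question also arises essentially only in Phase 1b, since Protocol 4.3 bars adults who could not tolerate the first challenge before a positive response.

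**Conclusion.** The concern holds and should be fixed. The protocol's within-person agreement statistic is absent from the SAP, the general remark in SAP 7.2 does not account for it, and the per-dose difference that remains measures group shift. Zero differences at every dose are compatible with kappa anywhere from −0.43 to 1.0 in the illustrative set.

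These sizes rest on assumed dose patterns, linear weights and, for the zero-difference cases, equal margins. The attrition figures apply only if unequal denominators are used, which the SAP neither states nor rules out. The planned outputs fail to distinguish repeatable from unrepeatable challenges only if the intervals are unpaired and the tables are for any dose. The consequence is limited to secondary objective 3.

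**What to change.** - **SAP 4:** define a Phase 1b paired set, the adults challenged in both Phase 1a and Phase 1b.
- **SAP 7.2.4, on that set:** one overall weighted kappa with stated weights and a 95% CI, over ordered first-positive-dose categories including no response. Add a coding rule for challenges stopped early without a positive response, a participant-level 1a-by-1b cross-tabulation of first positive dose, and each adult's dose shift.
- **Per-dose differences, if kept:** label them as systematic shift, compute them in the paired set with a named paired interval, and drop the boxplot, since one difference per dose has no distribution. A score-type interval avoids zero width when no pairs are discordant.
- **Protocol 13.4.3:** replace the per-category kappa with one overall statistic.
- **If the kappa was dropped on purpose:** say so and give the reason.

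The cost is SAP text and one protocol wording change, with no new data. The downside is imprecision. An assumed Phase 1b pattern of 4, 4, 5, 6, 6, 5, 7, 9, 9, 9 (five one-step shifts) gives kappa 1 − 0.5/2.28 = 0.78, with a bootstrap 95% CI of about 0.57 to 0.90.
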